#### **Exclusion Criteria**

1. Not applicable
2. Not applicable
3. Not applicable
4. Receipt of radiation therapy for bone metastasis within 2 weeks or any other radiation therapy within 4 weeks before crossover. Subjects with clinically relevant ongoing complications from prior radiation therapy that have not completely resolved are not eligible (eg, radiation esophagitis or other inflammation of the viscera)

5. Known brain metastases or cranial epidural disease unless adequately treated with radiotherapy and/or surgery (including radiosurgery) and stable for at least 4 weeks before crossover. Eligible subjects must be neurologically asymptomatic and without corticosteroid treatment at the time of crossover
6. Concomitant anticoagulation with oral anticoagulants (eg, warfarin, direct thrombin and Factor Xa inhibitors) or platelet inhibitors (eg, clopidogrel), except for the following allowed anticoagulants:
  - Low-dose aspirin for cardioprotection (per local applicable guidelines) and LMWH
  - Anticoagulation with therapeutic doses of LMWH in subjects without known brain metastases who are on a stable dose of LMWH for at least 6 weeks before crossover and who have had no clinically significant hemorrhagic complications from the anticoagulation regimen or the tumor
7. The subject has uncontrolled, significant intercurrent or recent illness including, but not limited to, the following conditions:
  - a. Cardiovascular disorders:
    - i. Congestive heart failure class 3 or 4 as defined by the New York Heart Association, unstable angina pectoris, serious cardiac arrhythmias
    - ii. Uncontrolled hypertension defined as sustained BP > 150 mm Hg systolic or > 100 mm Hg diastolic despite optimal antihypertensive treatment
    - iii. Stroke (including TIA), MI, or other ischemic event, or thromboembolic event (eg, DVT, pulmonary embolism) within 6 months before crossover. Subjects with a more recent diagnosis of DVT are allowed if stable, asymptomatic, and treated with LMWH for at least 6 weeks.
  - b. Gastrointestinal disorders (eg, malabsorption syndrome or gastric outlet obstruction) including those associated with a high risk of perforation or fistula formation:
    - i. Tumors invading the GI tract, active peptic ulcer disease, inflammatory bowel disease, ulcerative colitis, diverticulitis, cholecystitis, symptomatic cholangitis or appendicitis, acute pancreatitis or acute obstruction of the pancreatic or biliary duct, or gastric outlet obstruction
    - ii. Abdominal fistula, GI perforation, bowel obstruction, or intra-abdominal abscess.  
Note: Complete healing of an intra-abdominal abscess must be confirmed prior to crossover
  - c. Clinically significant hematemesis or hemoptysis of > 0.5 teaspoon (> 2.5 mL) of red blood or history of other significant bleeding within 3 months before crossover
  - d. Cavitating pulmonary lesion(s) or known endobronchial disease manifestation
  - e. Lesions invading major pulmonary blood vessels

- f. Other clinically significant disorders such as:
- Active infection requiring systemic treatment, infection with human immunodeficiency virus or acquired immunodeficiency syndrome related illness, or chronic hepatitis B or C infection
  - Serious non-healing wound/ulcer/bone fracture
  - Malabsorption syndrome
  - Moderate to severe hepatic impairment (Child-Pugh B or C)
  - Requirement for hemodialysis or peritoneal dialysis
  - Uncontrolled diabetes mellitus
  - History of solid organ transplantation
8. Complete wound healing from major surgery must have occurred 4 weeks before crossover and from minor surgery (eg, simple excision, tooth extraction) at least 10 days before crossover. Subjects with clinically relevant ongoing complications from prior surgery cannot be crossed over
9. Corrected QT interval calculated by the Fridericia formula (QTcF) > 500 ms within 28 days before crossover.  
*Note: If a single ECG shows a QTcF with an absolute value > 500 ms, two additional ECGs at intervals of approximately 3 min must be performed within 30 min after the initial ECG, and the average of these 3 consecutive results for QTcF will be used to determine eligibility.*
10. Pregnant or lactating females
11. Not applicable
12. Previously identified allergy or hypersensitivity to components of the study treatment formulations
13. Not applicable

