#### **4.3 Exclusion Criteria**

1. Prior treatment with any of the following:
  - a. Cabozantinib
  - b. Selective small-molecule BRAF kinase inhibitor (eg, vemurafenib, dabrafenib)
  - c. More than 2 VEGFR-targeting TKI agents (eg, lenvatinib, sorafenib, sunitinib, pazopanib, axitinib, vandetanib)
  - d. More than 1 immune checkpoint inhibitor therapy (eg, PD-1 or PD-L1 targeting agent)
  - e. More than 1 systemic chemotherapy regimen (given as single agent or in combination with another chemotherapy agent)
2. Receipt of any type of small molecule kinase inhibitor (including investigational kinase inhibitor) within 2 weeks or 5 half-lives of the agent, whichever is longer, before randomization
3. Receipt of any type of anticancer antibody (including investigational antibody) or systemic chemotherapy within 4 weeks before randomization
4. Receipt of radiation therapy for bone metastasis within 2 weeks or any other radiation therapy within 4 weeks before randomization. Subjects with clinically relevant ongoing complications from prior radiation therapy that have not completely resolved are not eligible (eg, radiation esophagitis or other inflammation of the viscera).
5. Known brain metastases or cranial epidural disease unless adequately treated with radiotherapy and/or surgery (including radiosurgery) and stable for at least 4 weeks before randomization. Eligible subjects must be neurologically asymptomatic and without corticosteroid treatment at the time of randomization.

6. Concomitant anticoagulation with oral anticoagulants (eg, warfarin, direct thrombin and Factor Xa inhibitors) or platelet inhibitors (eg, clopidogrel), except for the following allowed anticoagulants:
  - Low-dose aspirin for cardioprotection (per local applicable guidelines) and low-dose low molecular weight heparins (LMWH)
  - Anticoagulation with therapeutic doses of LMWH in subjects without known brain metastases who are on a stable dose of LMWH for at least 6 weeks before randomization and who have had no clinically significant hemorrhagic complications from the anticoagulation regimen or the tumor
  
7. The subject has uncontrolled, significant intercurrent or recent illness including, but not limited to, the following conditions:
  - a. Cardiovascular disorders:
    - i. Congestive heart failure class 3 or 4 as defined by the New York Heart Association, unstable angina pectoris, serious cardiac arrhythmias

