### **5.4.2 Extended Follow-up**

Following treatment discontinuation for whatever reason, subjects will continue to be followed either via clinic visit or telephone contact approximately every 12 weeks ( $\pm$  7 days) for the following information unless the subject withdraws consent for non-interventional study assessments:

- Survival status of the subject or date of death and primary cause of death
- Receipt of NPACTs: drug or procedure name and start/stop dates
- Information on subsequent progression following systemic NPACT (eg, date of subsequent radiographic progression or last known radiographic assessment)

Radiographic disease assessments and EQ-5D-5L are to continue in the Extended Follow-Up period as necessary per the schedule for these assessments in Appendix A, unless the subject withdraws from study interventions.

Subjects will be followed until death or until the Sponsor's decision to no longer collect these data.

At each contact, the investigator (or designee) will determine if the subject died, and if so, record the date and cause of death. All efforts must be undertaken by the study sites to determine the date of death (or date subject last known alive at the time of a data cut-off). This may include, but not necessarily be limited to, telephone contacts, communication at study visits, registered letters, and reviews of local obituaries and government death records (where allowed by local regulations). If subject is lost to follow-up, multiple attempts to contact must be made and documented in the subject records.

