Radiographic tumor assessments are to continue until the later of investigator-assessed radiographic disease progression per RECIST 1.1 that is confirmed per real-time BIRC review or the date of the decision to permanently discontinue study treatment; however, radiographic tumor assessments may cease at the time of first systemic NPACT, if given before these milestones occur. Bone scan evaluations will end on the date of last CT/MRI scan. If the bone scan schedule does not coincide with the last CT/MRI scan, no additional bone scan is needed after the last CT/MRI scan has been performed.

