### **7.1.2 Prohibited or Restricted Therapies**

*The following therapies are prohibited until study treatment has been permanently discontinued:*

- Any investigational agent or investigational medical device.
- Therapeutic doses of oral anticoagulants (eg, warfarin or other coumarin-related agents, direct thrombin or direct FXa inhibitors, or antiplatelet agents such as clopidogrel, or chronic use of aspirin above low dose levels for cardioprotection per local applicable guidelines).
- Any nonprotocol systemic anticancer treatment (eg, chemotherapy, immunotherapy, radionuclides, drugs or herbal products used specifically for the treatment of DTC).

*The following therapies should be avoided until study treatment has been permanently discontinued or until otherwise specified:*

- Local anticancer treatment including palliative radiation, ablation, embolization, or surgery with impact on tumor lesions should not be performed until radiographic progression per RECIST 1.1 has been established. If clinically unavoidable the investigator should consult the Sponsor prior to the procedure for safety guidance.
- Erythropoietic stimulating agents (eg, epoetin alfa and darbepoetin alfa) should not be used based on a report of increased risk of tumor recurrence/progression associated with erythropoietin (Wright et al 2007).
- Concomitant medications that are known to prolong the QTc interval should be avoided in subjects who receive cabozantinib until they have permanently discontinued cabozantinib treatment (refer to <http://www.qtdrugs.org> for a list of drugs which have the potential to prolong the QTc interval).
- Chronic co-administration of cabozantinib with strong inducers of the CYP3A4 family (eg, phenytoin, carbamazepine, rifampin, rifabutin, rifapentine, phenobarbital, and St. John's Wort) may significantly decrease cabozantinib concentrations and should be avoided. Selection of alternate concomitant medications with no or minimal CYP3A4 enzyme induction potential is recommended. See Appendix E for further details.
- Caution must be used when discontinuing treatment with a strong CYP3A4 inducer in a subject who has been concurrently receiving a stable dose of cabozantinib, as this could significantly increase the exposure to cabozantinib.

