### **Eligibility Criteria for Crossover to Cabozantinib Following Treatment with Placebo**

(Note that the numbering of the criteria is maintained from the start of the study [Section 4.2 Inclusion Criteria and Section 4.3 Exclusion Criteria]. “Not applicable” rows below refer to eligibility criteria from the start of the study that are not relevant for the Crossover Phase as these subjects have either already fulfilled the criteria upon study entry, or the criteria are not a requirement for the Crossover Phase.)

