#### 8.4.4 Time to Second Disease Progression or Death (PFS2)

The time to second disease progression or death (PFS2) is defined as the time from randomization to the date of the earliest of the following events: start of second subsequent non-radiation anti-cancer therapy, second objective disease progression, or death. For placebo subjects who have crossed over to receive cabozantinib, cabozantinib will be considered as the first subsequent therapy. For subjects randomized to cabozantinib who continue on study treatment after their first disease progression, the start date of their first subsequent therapy will be considered to be a potential event date. Subjects alive and for whom a PFS2 event has not been observed will be censored at the last time known to be alive. The definition of event dates for PFS2 is provided in the table below.

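### Appendix B drops the systemic-therapy washouts at crossover: harmless on the direct route, but no minimum interval is set for a placebo subject who stopped treatment and then took systemic anticancer therapy

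*Combined protocol and SAP*

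**What the plan says.** **Entry.** Section 4.3, exclusion 2, excludes subjects who received a small-molecule kinase inhibitor "within 2 weeks or 5 half-lives of the agent, whichever is longer, before randomization". Exclusion 3 sets 4 weeks after an anticancer antibody or systemic chemotherapy. Exclusion 4 sets the radiation washout.

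**Crossover.** Appendix B lists exclusions 2 and 3 as not applicable. It explains that label as covering criteria that subjects "have either already fulfilled the criteria upon study entry, or the criteria are not a requirement for the Crossover Phase". Exclusion 4 is kept and counted back from crossover: "Receipt of radiation therapy for bone metastasis within 2 weeks or any other radiation therapy within 4 weeks before crossover". The windows for brain-metastasis stability, thromboembolic events, bleeding, wound healing and QTcF are likewise tied to crossover.

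**On treatment.** Section 7.1.2 lists systemic NPACT among the treatments for which it says that these "therapies are prohibited until study treatment has been permanently discontinued". Local treatment is handled more loosely: "Local anticancer treatment including palliative radiation, ablation, embolization, or surgery with impact on tumor lesions should not be performed until radiographic progression" is established, with an exception where it is clinically unavoidable.

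**Off treatment.** Section 5.4.2 has sites record, after discontinuation, "Receipt of NPACTs: drug or procedure name and start/stop dates". Table 20-1 footnote c asks for an interval history from placebo subjects screened for crossover who stopped blinded treatment more than 30 days before the first crossover dose. Appendix B keeps crossover screening open until the transition to the Maintenance Phase.

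**The concern.** A washout depends on time. Meeting it at randomization says nothing about therapy started afterwards, so the explanation that a criterion was fulfilled at entry does not cover a systemic agent taken between stopping placebo and starting cabozantinib. The protocol judged such overlap worth excluding at entry, and the drug and starting dose at crossover are the same.

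The case is clinically plausible. Section 1.3 describes sorafenib and lenvatinib as approved for this disease, while inclusion 4 requires prior use of only one of them. A subject could therefore take the other as NPACT. Both inhibit VEGFR, as cabozantinib does. Starting cabozantinib on top of residual drug fits poorly with Section 1.5.5, which says the crossover criteria are meant to keep out subjects with predisposing risks.

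**Working it through.** The plan states no figure on this point. The check is a side-by-side reading, followed by simple arithmetic.

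**1. Minimum interval from last therapy to study drug**

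| Prior therapy | Before randomization (4.3) | Before crossover (Appendix B) |
|---|---|---|
| Kinase inhibitor | longer of 14 days or 5 half-lives | none stated |
| Antibody or chemotherapy | 28 days | none stated |
| Radiation to bone | 14 days | 14 days |
| Other radiation | 28 days | 28 days |

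No replacement for the two missing intervals appears in Sections 3.6.1, 5.2, 5.3, 5.7.6.2 or 7.1.2, the Table 20-1 footnotes, Appendix C, or SAP 4.1 and 8.4.4.

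**2. Direct route.** The subject has taken placebo only. Systemic NPACT is barred on study treatment, whereas radiation may be given after progression, or earlier if unavoidable. Recent radiation is therefore possible at crossover and recent systemic therapy is not. Keeping exclusion 4 and dropping 2 and 3 is coherent here.

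**3. Off-treatment route.** Footnote c covers subjects who have been off blinded treatment for some time. Section 5.7.6.2 allows for last scans more than 8 weeks old at the first crossover dose. SAP 4.1 attaches its condition of still being on treatment to discontinuation, not to crossover. Section 5.4.2 expects NPACT after discontinuation. No deadline is set between confirmed progression and crossover, so progression, stopping placebo, NPACT and then crossover is not excluded by any sentence. Nor does any passage describe that sequence.

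**4. What the interval is worth (illustration only).** Assume first-order elimination and half-lives of 1, 2.8 and 5 days; the documents give none. The fraction remaining is 0.5^(t / half-life). The entry rule gives t = max(14, 5 × half-life), and the two limits meet at a half-life of 14/5 = 2.8 days.

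| Half-life | Cabozantinib 1 day after last dose | Under the entry rule |
|---|---|---|
| 1 day | 0.5^1 = 50% | 0.5^14 = 0.006% |
| 2.8 days | 0.5^(1/2.8) = 78% | 0.5^5 = 3.1% |
| 5 days | 0.5^(1/5) = 87% | 0.5^5 = 3.1% (t = 25 days) |

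The 1-day gap is a chosen worst case, not an expectation.

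**5. Fit with the 8-week crossover window after study-wide unblinding** (56 days), for an agent stopped on the unblinding date. A 14-day washout leaves 56 − 14 = 42 days. A 28-day washout leaves 56 − 28 = 28 days. Five half-lives exceed 56 days only if the half-life exceeds 56/5 = 11.2 days.

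**The case against.** The best reply is that the plan already closes the route. The systemic ban ends only at permanent discontinuation of study treatment, while footnote c speaks of stopping blinded treatment. Crossover cabozantinib is itself study treatment, so a subject off placebo but still a crossover candidate may remain under the ban. A subject who needs systemic NPACT has met a discontinuation reason in Section 3.6.1.

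The rest of the plan fits that reading. After confirmed progression Section 5.3 gives a placebo subject two options: cross over, or stop study treatment and enter follow-up. Before progression, "radiographic tumor assessments may cease at the time of first systemic NPACT, if given before these milestones occur", so a later progression trigger is unlikely. SAP 8.4.4 states: "For placebo subjects who have crossed over to receive cabozantinib, cabozantinib will be considered as the first subsequent therapy". Footnote c has an ordinary explanation, since placebo may stop while confirmation, unblinding and consent are completed.

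This makes the route less likely, and it means the ban cannot simply be said to end when placebo stops. It does not close the gap, because no sentence bars return after NPACT. The PFS2 rule is an analysis convention, not an eligibility bar.

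Existing safeguards also count. The medical monitor authorizes individual unblinding, crossover has its own consent, and NPACT dates are recorded. Toxicity recovery, ECOG 0-1, laboratory limits within 7 days and QTcF are checked again, and footnote f calls for extra tests if deterioration is suspected. These detect manifest toxicity and leave room for judgment, but none sets an interval.

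A last objection is that writing in a washout would endorse NPACT followed by cabozantinib, against the PFS2 convention. But the text already leaves that sequence open, and a washout would only make it safer.

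**Conclusion.** The point holds in narrow form, as a minor patient-safety improvement. Exclusions 2 and 3 are waived at crossover without exception. That is harmless on the direct route but leaves no fixed interval for a placebo subject who is off treatment and has since taken systemic NPACT.

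A reader might infer more: that crossover subjects generally start cabozantinib without washout, or that the plan provides for NPACT followed by crossover. The documents support neither. Direct-route subjects have no systemic agent to wash out, and the NPACT route is put together from several provisions and appears not to have been expected.

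The size in the documents is the difference in intervals: at least 14 days or 28 days at entry, none at crossover. The residual-drug percentages rest on assumed half-lives and a chosen gap, and the conclusion does not depend on them. The number of subjects cannot be estimated, because no NPACT rate is given. Among about 100 placebo subjects it is probably very small.

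The primary endpoints are unaffected. Section 9.11 keeps crossover data out of the primary evaluation, and systemic NPACT before an event already censors PFS.

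**What to change.** In Appendix B, replace the not-applicable entries for crossover exclusions 2 and 3 with the Section 4.3 wording, counted back from crossover instead of randomization. Leave exclusion 1 as it is. Direct-route subjects meet the restored criteria automatically, and no analysis changes.

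The cost is two lines of text, but Section 13 requires IRB/EC submission and approval, and Section 3.1 foresees about 150 sites. It should therefore go into the next amendment and does not justify one of its own. The downside for subjects is a short delay for the rare one with recent systemic NPACT. The arithmetic above shows that this normally fits the 8-week window.

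If the sponsor's intention is that systemic NPACT ends crossover eligibility, one sentence saying so would also close the gap and would match the PFS2 rule. It would, however, deny cabozantinib to those subjects rather than delay it.

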### 7.1.1 Allowed Therapies

- Antiemetics and antidiarrheal medications are allowed prophylactically according to standard clinical practice if clinically indicated.
- Granulocyte colony-stimulating factors (G-CSF or GM-CSF) are allowed if used per clinical guidelines (eg, ASCO or ESMO guidelines).
- Bisphosphonates or denosumab can be used to control bone loss or hypercalcemia if the benefit outweighs the risk per the investigator's discretion (Section 6.7.9).

Note: osteonecrosis of the jaw has been reported in subjects using bisphosphonates or denosumab. Oral examinations are recommended at screening to determine eligibility and periodically during the study. In addition, subjects should be advised regarding oral hygiene practice and to quickly report symptoms to the investigator. Frequent monitoring for potentially overlapping toxicities with study treatment is recommended.

- Transfusions and hormone replacement (including TSH-suppressive thyroid hormone therapy) should be utilized as indicated by standard clinical practice.

- Individualized anticoagulation therapy with heparin is allowed if it can be provided safely and effectively under the following circumstances:
  - *Low dose low molecular weight heparins (LMWH) for prophylactic use* are allowed if clinically indicated and the benefit outweighs the risk per the investigator's discretion.
  - *Therapeutic doses of LMWH at the time of the first dose of study treatment* are allowed if the subject has no evidence of brain metastasis, has been on a stable dose of LMWH for at least 6 weeks, and has had no complications from a thromboembolic event or the anticoagulation regimen.
  - *Therapeutic doses of LMWH after first dose of study treatment* are allowed if clinically indicated (eg, for the treatment of DVT), and the benefit outweighs the risk per the investigator's discretion. For management of thromboembolic complications while on study, refer to Section 6.7.5.
  - Accepted clinical guidelines regarding appropriate management while receiving anticoagulation therapy with heparins must be followed. This includes, but is not limited to, subject education regarding potential adverse drug reactions, monitoring laboratory parameters, dose adjustments (eg, due to kidney dysfunction).
  - For restrictions on oral anticoagulants see Section 7.1.2.

Potential drug interactions with cabozantinib are summarized in Section 7.1.2.1 and are discussed in more detail in the Investigator's Brochure.

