**Table 20-1: Schedule of Assessments Crossover Phase**

This schedule is to be followed for subjects who crossover from the placebo arm to receive cabozantinib. W1D1 will be the first day of crossover cabozantinib treatment. In the absence of toxicity, all scheduled safety visits should occur within  $\pm 3$  days of the nominal time for the first 9 weeks and within  $\pm 5$  days of the nominal visit day thereafter, unless otherwise indicated. If study treatment is interrupted or missed after W1D1, assessments should continue following the schedule described below.

|  | Crossover Screening (before crossover) a | W1D1   | W3D1 ( $\pm 3$ d) | W5D1 ( $\pm 3$ d) | W7D1 ( $\pm 3$ d) | W9D1 ( $\pm 3$ d) | Beyond Week 9 ( $\pm 5$ d)        | 30-day Post-Treatment Follow-Up (+14 d) | Extended Follow-Up |
|--|---|--|-------------------|-------------------|-------------------|-------------------|-----------------------------------|---|--------------------|
| Informed consent (Section 12.2)  | X b                                      |  |                   |                   |                   |                   |                                   |   |                    |
| Interval medical history   | X c                                      |  |                   |                   |                   |                   |                                   |   |                    |
| Physical exam (PE) + weight (Section 5.7.2)                                | $\leq 7$ days                                       | X (prior to first dose; symptom-directed PE) | X                 | X                 | X                 | X                 | Every 4 wks (W13D1, W17D1 etc)    | X                                       |                    |
| Vital signs (Section 5.7.3)  | $\leq 7$ days                                       | X (prior to first dose)                      | X                 | X                 | X                 | X                 | Every 4 wks (W13D1, W17D1 etc)    | X                                       |                    |
| ECOG performance status (Section 5.7.2)                                    | $\leq 7$ days                                       | X (prior to first dose)                      | X                 | X                 | X                 | X                 | Every 4 wks (W13D1, W17D1 etc)    | X                                       |                    |

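### Crossover exclusion 6 in Appendix B drops the low-dose qualifier on LMWH that Section 4.3 and the synopsis carry: a minor inconsistency in a safety criterion

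*Combined protocol and SAP*

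**What the plan says.** Exclusion 6 appears three times: in the synopsis, in Section 4.3 and, for crossover, in Appendix B. The Appendix B lead-in is "Concomitant anticoagulation with oral anticoagulants (eg, warfarin, direct thrombin and Factor Xa inhibitors) or platelet inhibitors (eg, clopidogrel), except for the following allowed anticoagulants". Two bullets follow.

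- **First bullet.** Section 4.3 and the synopsis have "Low-dose aspirin for cardioprotection (per local applicable guidelines) and low-dose low molecular weight heparins (LMWH". Appendix B has "Low-dose aspirin for cardioprotection (per local applicable guidelines) and LMWH".
- **Second bullet.** All three versions permit therapeutic LMWH under conditions. In Appendix B it is permitted "in subjects without known brain metastases who are on a stable dose of LMWH for at least 6 weeks before crossover", and only if there has been no important bleeding from the anticoagulant or the tumor.

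Section 7.1.1 also deals with LMWH. One bullet covers "Therapeutic doses of LMWH at the time of the first dose of study treatment"; such doses "are allowed if the subject has no evidence of brain metastasis, has been on a stable dose of LMWH for at least 6 weeks", with a further condition on complications. The next bullet covers therapeutic LMWH started later; such doses "are allowed if clinically indicated (eg, for the treatment of DVT), and the benefit outweighs the risk", as judged by the investigator, with no limit for brain metastases.

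**The concern.** The first bullet in Appendix B puts no dose limit on LMWH. The bullets are alternative allowances, so a subject who satisfies the first does not need the second. On that reading the brain-metastasis, 6-week and bleeding limits on therapeutic LMWH no longer do anything at crossover.

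The matter at stake is bleeding. Section 1.5.5 gives the purpose of the crossover criteria as keeping out subjects with predisposing risks for cabozantinib. Section 6.7.4 reports serious and sometimes fatal hemorrhage, and says that the risk with brain metastases has not been fully examined. A criterion that two sites can apply in opposite ways to the same subject does not serve that purpose well.

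**Working it through.** The plan gives no figure on this point and no arithmetic on rates is possible, so the check compares text.

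**Step 1. The three versions of exclusion 6.**

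| Version | Low-dose before LMWH | Conditional therapeutic bullet kept |
|---|---|---|
| Synopsis | yes | yes |
| Section 4.3 | yes | yes |
| Appendix B (crossover) | no | yes, re-dated to crossover |

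The qualifier is present in 2 of 3 versions, and the second bullet in 3 of 3.

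**Step 2. Two readings of the Appendix B first bullet.** If *low-dose* governs both aspirin and LMWH, Appendix B agrees with Section 4.3 and both bullets have a job. If it governs aspirin alone, any LMWH dose is allowed and the second bullet is redundant. A reading that leaves a retained, re-dated condition without function is the less likely one.

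**Step 3. What else would protect the subject under the literal reading?**

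| Second-bullet limit | Other crossover criterion | Coverage |
|---|---|---|
| No known brain metastases | 5: admits metastases if treated, stable for 4 weeks, asymptomatic and off corticosteroids | partial |
| Stable LMWH dose for at least 6 weeks | 7.a.iii: at least 6 weeks of LMWH, but only for a DVT within 6 months; pulmonary embolism within 6 months is excluded | partial |
| No important bleeding on anticoagulant or from tumor | 7.c: significant bleeding within 3 months | partial |

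None of the 3 limits is fully replaced; all 3 are partly covered. The main residual case is treated, stable brain metastases together with therapeutic LMWH. It can arise on placebo: Section 6.7.5 prefers LMWH for thrombotic events, and the later bullet of Section 7.1.1 permits it without a brain-metastasis limit.

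**Step 4. Does Section 7.1.1 settle it?** Its stricter bullet applies at the first dose of study treatment. Section 5 equates that dose with W1D1, and Section 5.2 defines W1D1 as the first day of blinded treatment, placebo included. For crossover, however, Table 20-1 states that "W1D1 will be the first day of crossover cabozantinib treatment". On the first definition a crossover subject falls under the looser bullet; on the second, under the stricter one. The section does not clearly decide the matter.

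**Step 5. Could a site be sure that this is a slip?** Not entirely. Appendix B changes the content of other criteria without comment: the laboratory window is 7 days instead of 10, the 8-week limit after major surgery is gone, and the 6-month window in 7.b.ii is gone. A missing qualifier could be taken for one more intended change.

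**The case against.** The strongest reply is that the criterion resolves itself. The second bullet names therapeutic LMWH specifically and was deliberately re-dated to crossover, and a specific condition should prevail over an unqualified word. Appendix B marks dropped criteria as not applicable, and criterion 6 is not so marked. This stands as evidence of intent. It is why a reader who infers that the sponsor chose to relax the LMWH rule at crossover goes too far: nothing in the documents states or explains such a choice.

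A second reply is that literal reading proves too much. The lead-in excludes only oral anticoagulants and platelet inhibitors, so strictly read it never excludes LMWH, in Section 4.3 either. This is fair. The bullets have to be read as limits in both places for the rule to work at all. Read so, Section 4.3 is clear and Appendix B is not.

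A third reply is that the plan already accepts similar exposure on treatment. Section 7.1.1 allows therapeutic LMWH after the first dose, and Section 6.7.5 lets treatment resume on anticoagulation after an uncomplicated clot. Criterion 7.a.iii also catches many clots that occur on placebo. With the design's assumed placebo median PFS of 5.5 months and exponential times, 1 − 0.5^(6/5.5) = 1 − 0.469, or about 53%, of placebo subjects would have progressed or died by 6 months. For those who cross over soon after progressing in that time, any clot on placebo lies within or close to the 6-month look-back. This lowers the stakes considerably. It does not remove the residual case, because a stable, asymptomatic DVT with at least 6 weeks of LMWH passes 7.a.iii whether or not brain metastases are present.

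**Conclusion.** Wrong as written, at low severity. This is an internal inconsistency in an operative safety criterion, not a design choice. Appendix B exclusion 6 lacks one word that its two counterparts have. Taken literally, that makes the limits on therapeutic LMWH redundant, although the retained second bullet shows that they were most likely meant to bind.

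The number of subjects affected is unknown, probably small, and may be zero. The documents give no rate of therapeutic LMWH use or of crossover. The Phase 2 study in Section 1.4.1.2.1 had brain metastases at entry in 20% of subjects, but that does not estimate how many would also be on therapeutic LMWH at crossover.

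A reader might infer that the trial's results are at risk. They are not. Crossover needs progression confirmed by the BIRC, or comes with the study-wide unblinding after the primary endpoints have been analyzed. Section 9.11 keeps crossover data out of the primary evaluation of either arm. PFS and ORR are untouched; the effect is confined to eligibility and safety in the Crossover Phase.

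The conclusion assumes that the exclusion 6 bullets are meant as limits on LMWH, in Section 4.3 and Appendix B alike.

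**What to change.** In Appendix B, crossover exclusion 6, first bullet, write low-dose LMWH, as in Section 4.3. The second bullet stays as it is and then governs therapeutic doses at crossover. Carry the same word into any crossover eligibility checklist.

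The cost is one word in a protocol amendment or clarification. No subjects, procedures or analyses are added, and at most a few subjects' crossover eligibility would change.
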